### **Intervention plan of the intervention arm**

The intervention plan contains three parts: (1) individual intervention; (2) insulin injection follow-up management; (3) motivational group activities. Different

intervention strategies are applied to patients according to their stages of change. In addition, a computerized information system will be applied to facilitate data management and recording by interveners. The strategies for individual intervention designed according to the stage of change and the corresponding process of change are shown in Table 2. Details of insulin injection follow-up management from preparation stage to maintenance stage are shown in Table 3. The motivational group activities from precontemplation stage to maintenance stage are shown in Table 4.

### **Usual care of the control arm**

Participants in the control arm attend regular patient education at the hospital.

The contents of the education plan are as follows:

1. Teach participants the method of injection following the standard procedure, including gathering insulin supplies, the steps of injection, and so on.
2. Hand out a step-by-step pictorial guide to participants after teaching them the techniques and supply preparation for using insulin pen. Fill in the type and dose of insulin and the site and time of injection on a sheet for participants and their family to refer to after they return home.
3. Recommend patients to administer blood-glucose self-monitoring and record the results.
4. Conduct a telephone follow-up 3 days after patient education to check on the condition of insulin injection. Schedule a return visit after a week, during which the doctor adjusts the medication according to the results of SMBG and instructs the rule for dose adjustment at home.
5. Provide a hotline for patients to seek consultation when they encounter difficulties or problems.
6. Play patient education video clips on insulin injection in the waiting room when patients come for return visits.

7. Provide patient education in small groups occasionally, in which insulin-treated patients are invited to share their experience and clarify questions.

### **Ethical consideration**

The study is approved by the Human Experiment and Ethics Committee of two hospitals (NO. KMUHI-E(I)-20150262, TSGHIRB-1-105-05-163). Participants are informed of their rights to refuse participation in the study without any penalty. Only after the participants have signed the consent forms will data be collected from participants.

### **Data Analysis**

The statistical software program SPSS 17.0 was used for data analysis. The Chi-squared test and independent t-test were used to compare differences in personal characteristics and outcome variables between the two groups before and after intervention. Paired t-tests were used to examine within-group differences at baseline, 3 months, 6 months, and 12 months post-intervention. A linear mixed-effect model that adjusted for the demographic data and baseline outcome variables was used to examine the changing amount of outcome variables from baseline to 3 months, to 6 months, and to 12 months post-intervention between the intervention and control arms. Participants were considered as a random effect. First-order autoregressive was used in the mixed-effect model analysis with the restricted maximum likelihood (REML) approach. A  $p$ -value  $< .05$  was considered statistically significant.

Table 1. Outcome measures and collection time points

Measures	Baseline	3 rd month	6 th month	12 th month
Demographic data & disease characteristics	✓	✓	✓	✓
Body mass index	✓	-	✓	✓
HbA1c	✓	✓	✓	✓
Lipids (TC, HDL-C, LDL-C, TG)	✓	✓	✓	✓
Renal function: UACR, GFR	✓	✓	✓	✓
Stage of change for insulin injection	✓	✓	✓	✓
Insulin injection adherence	-	✓	✓	✓
Appraisal of insulin injection	✓	✓	✓	✓
Empowerment	✓	-	✓	✓
Self-efficacy	-	✓	✓	✓
Diabetes distress	✓	-	✓	✓
Quality of life	✓	-	✓	✓

Table 2. Individual intervention plan

Stage of Change	Strategy	Process of Change
Precontemplation	
 
• Use examples in which good/bad glycemic control has a positive/negative impact on significant others to help patients reflect on their own HbA1c control
 
• Explain current health condition to patients through the changes in the curves of the their data
 
• Use UKPDS Risk Engine to predict the risk of cardiovascular disease and cerebrovascular event in the future 10 to 20 years in individual patients
 
	Consciousness raising
	
 
• Build a well-established trusting relationship
 
• Use empathic skills to recognize the feelings of patients (fear, worry, guilt, etc.)
 
• Guide patients to explore the influence of glycemic control and physical health on their lives
 
• Explain that accepting insulin injection does not mean failure of treatment or advancement of disease but the natural progression of diabetes
 
• Assess the decisional balance for insulin injection and provide clarification
 
• Guide patients to think about possible benefits brought about by insulin injection to themselves and their family
 
	Dramatic relief
Contemplation	
 
• Invite patients to compare the perceived pros and cons
 
	Self-reevaluation

	
 
List all medications for treating diabetes and their mechanisms, maximum dose, expected range of improvement in HbA1c, possible side effects, and costs
 
	
	
 
Enhance the positive effects of insulin injection
 
Guide patients to consider the importance of good glycemic control
 
	Dramatic relief
Preparation	
 
Assess the decisional balance for insulin injection and provide guidance
 
	Dramatic relief
	
 
Set short-term targets for glycemic control and insulin injection with patients
 
	Self-reevaluation
	
 
Assess family support and provide patient education
 
Provide resources that give instant feedback and build a platform for instant interaction
 
	Helping relationship
	
 
Systematic desensitization—Gradual self-administered insulin injection. Patients first receive insulin injection given by healthcare professionals at medical institutions, and then slowly perform injection by themselves from withdrawing insulin, pushing away air bubbles, and injecting. Give rewards for each progress made
 
Instruct patients in the techniques for insulin injection and medicine preservation
 
Use the results of blood-glucose self-monitoring to guide patients to
 
	Counterconditioning

---

	
think about the relationship between insulin injection, diet, and physical activity
 
 
• Provide patient education on blood-glucose self-monitoring and assessment on the ability to deal with hypoglycemia
 
• Ask patients to continuously keep a daily record of the dose, time, site of injection, administration of blood-glucose self-monitoring, and incidents of hypo/hyperglycemia in the “Health Guardian Pamphlet”
 
	
Action	
 
• Educate family members to provide support for patients
 
• Build an instant online interactive system with professionals to provide feedback to patients
 
	Helping relationship
	
 
• Encourage patients to adhere to the insulin injection plan
 
• Healthcare professionals conduct telephone interviews and schedule return visits for patients on a regular basis
 
• Instruct patients how to adjust their diet and exercise flexibly according to insulin injection so as to decrease the chance of termination caused by barriers
 
• Teach patients to adjust the dose of insulin according to the results of blood-glucose self-monitoring
 
	Reinforcement management
	
 
• Patients promise to set mid-term and long-term goals
 
	Self-liberation

---

[figure not shown]
Table 3. Motivational group activity

Stage of Change	Strategy	Process of Change
Precontemplation	
 
• Listen to fellow patients in the stages of action and maintenance share the benefits of insulin injection and the ways to overcome obstacles
 
• Try out insulin injection
 
• Use pictorial or multimedia materials to illustrate the relationship between insulin and blood-glucose
 
	Self-reevaluation
Preparation	
 
• Listen to fellow patients in the stages of action and maintenance share the benefits of insulin injection and the ways to overcome obstacles
 
• Try out insulin injection
 
• Use pictorial or multimedia materials to illustrate the relationship between insulin and blood-glucose
 
	Self-reevaluation
Action	
 
• Share experience in insulin injection and provide support and solution
 
• Build mutually supportive partnerships with fellow patients
 
	Reinforcement management
Maintenance	
 
• Share successful experience with other patients to enhance the motivation of the patient to continue insulin injection
 
	Reinforcement management

Table 4. Insulin injection follow-up management

Stage of Change	Strategy	Process of Change
Preparation	
 
• Follow up problems with insulin injection, e.g. dose, site of injection, and technique
 
	Reinforcement management
Action	
 
• Guide patients to examine the relationship between insulin injection and changes in blood-glucose to strengthen their self-efficacy
 
	Self-reevaluation
	
 
• Ask patients to continuously keep a daily record of the dose, time, site of injection, administration of blood-glucose self-monitoring, and incidents of hypo/hyperglycemia in the “Health Guardian Pamphlet”
 
	Counterconditioning
Maintenance	
 
• Encourage patients regularly when HbA1c level decreases
 
• Provide care and support
 
	Reinforcement management

Figure 1. Intervention flowchart of the intervention arm

\* Motivational group activities are held once every two months. Patients in the stages of action and maintenance will be invited to share their experiences during the activity.

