## **Methods**

### **Study design**

The present study adopts quasi-experimental design. To avoid contamination between participants in two study arms, cluster sampling is used. Patients with T2DM of an endocrinology clinic in southern Taiwan are assigned to the intervention arm, whereas patients at another endocrinology clinic in southern Taiwan are placed in the control arm. Eligible patients that match the inclusion criteria are recommended by doctors to initiate insulin treatment after getting the consent forms from eligible participants. Research assistants will subsequently collect baseline data from eligible participants. Afterwards, the participants in the intervention arm will receive the intervention. For the control arm, the participants will receive regular patient education originally administered at the hospital. Data for the participants in both study arms will be collected by research assistants at baseline, 3 months, 6 months, and 12 months post-intervention. The main outcome variable is change in HbA1c levels, while the change in stage of change, in insulin injection adherence, in appraisal of insulin injection, in patient empowerment, in self-efficacy for insulin injection, in diabetes distress, in quality of life, in triglyceride(TG), in total cholesterol (TC), in high-density lipoprotein cholesterol(HDL-C), in low density lipoprotein cholesterol(LDL-C), in urine albumin creatinine ratio (UACR), in estimated glomerular filtration rate(GFR) are secondary outcome variables. The outcome

variables and collection time points are summarized in Table 1.

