### *Demographic data & disease characteristics*

Age, sex, educational level, duration of diabetes, duration of taking oral drug before insulin therapy will be collected at baseline. Insulin treatment regimen including type of insulin, dose, frequency of injection and blood sugar self-monitoring will be collected after participants receiving insulin injection.

*Stage of change for insulin injection.* A question of stages of change for insulin injection was developed. At baseline, the question was “If the doctor recommends that you initiate insulin treatment right now, what would be your opinion?” Three responses to this question included “never considered”, “under consideration and might start within the next 6 months”, and “likely to start immediately”, which respectively represented three early stages of change — precontemplation, contemplation, and preparation. At the 3, 6, and 12 months post-intervention, the question was “what’s the status of your insulin injection?” The responses were “taking insulin injection previously, but now is stop insulin injection and never consider to receive insulin injection again”, “taking insulin injection previously, but now is stop insulin injection, consider to start insulin injection again within next 6 months”, “still receive insulin injection but sometimes forget to inject” , “Continuously inject insulin but less than 6 months”, “Continuously injected insulin and more than 6 months”.

*Insulin injection adherence.* An 8-item Morisky Medication Adherence Scale was used to assess insulin injection adherence behaviors of participants. The total scores ranged from 7 to 11. The higher scores indicate, the better insulin injection adherence behaviors

*Appraisal of insulin injection.* A 13-item Decisional Balance for Insulin Injection scale was used in the study to assess the appraisal of insulin injection. The scale comprised subscales of positive and negative appraisal. Each item was rated from 1 (strongly

disagree) to 5 (strongly agree). Decisional balance for insulin injection was calculated by deducting the mean score of positive appraisal with that of negative appraisal. The higher score indicated the higher decisional balance for insulin injection.

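### No ordinal method is named for stage of change; if the listed chi-squared test is used, the order of the stages is ignored and power against a consistent ordered shift is lower

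*Combined protocol and SAP*

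**What the plan says.** The Study design section makes stage of change a secondary outcome, expressed as a change: "The main outcome variable is change in HbA1c levels, while the change in stage of change, in insulin injection adherence".

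The Measurements section describes the item, under the heading on demographic data and disease characteristics. At baseline one question has three answers, "which respectively represented three early stages of change — precontemplation, contemplation, and preparation". At 3, 6 and 12 months a different question has five answers. They begin with having stopped and ruling insulin out, and end with "Continuously inject insulin but less than 6 months" and "Continuously injected insulin and more than 6 months". No score is attached to any answer.

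The Data Analysis section gives two kinds of between-arm analysis. The first is cross-sectional: "The Chi-squared test and independent t-test were used to compare differences in personal characteristics and outcome variables between the two groups before and after intervention". The second is longitudinal: "A linear mixed-effect model that adjusted for the demographic data and baseline outcome variables was used to examine the changing amount of outcome variables". Neither sentence says which outcome goes with which method. No rank test, trend test or ordinal regression is mentioned.

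**The concern.** The trial rests on a theory of movement through stages, so the question about this outcome is directional: does the intervention arm end up further along? Pearson's chi-squared test treats the categories as unordered. Its p-value stays the same if the stages are shuffled, and it spreads the evidence over one degree of freedom fewer than there are categories: 4 with five answers, 2 with three.

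This has two consequences if that test is used. A consistent shift to later stages is harder to detect than with a test of the same data that uses the order. A significant result also need not mean a shift: it can arise because patients gather in a middle category with no net movement. What is at stake is efficiency and interpretation for one secondary outcome. Validity is not in question, since both kinds of test hold their error rate.

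**Working it through.** **1. Which listed method fits.** The other outcomes are laboratory values or scale scores, which suit the t-test and the mixed model. Stage of change is a set of named answers without scores, so of the two cross-sectional tests only chi-squared fits it as recorded. The mixed model analyses an amount of change from baseline. The baseline item has three answers to one question and the follow-up item has five answers to another, with no common score, so that change is not defined as the plan stands.

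**2. The plan's own figure.** The Samples section gives effect size 0.5 (for HbA1c), alpha 0.05 and power 0.8. Two-sided: n = 2 × (1.960 + 0.842)² / 0.5² = 62.8, so 63 per arm, as stated. With attrition, 63 × 1.2 = 75.6, so 76, also as stated. I use 63 analysed per arm.

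**3. Assumptions the documents do not supply.** The plan gives no stage distribution and no effect size for stage. I assume control-arm shares and a shift of 0.5 SD on a normal scale underlying the answers, borrowing the HbA1c value. For cut points c_j of the control distribution, the cumulative intervention share is Φ(c_j − 0.5).

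**4. One case by hand.** Five equal control shares of 0.20 become 0.0899 / 0.1358 / 0.1770 / 0.2311 / 0.3663.
- Chi-squared: the noncentrality is n Σ (p − q)² / (p + q) = 63 × (0.0418 + 0.0123 + 0.0014 + 0.0022 + 0.0488) = 63 × 0.1066 = 6.71. With 4 degrees of freedom and critical value 9.49, power is about 0.52.
- Rank-sum: the chance that an intervention patient is in the later stage, counting ties as half, is 0.0899 × 0.1 + 0.1358 × 0.3 + 0.1770 × 0.5 + 0.2311 × 0.7 + 0.3663 × 0.9 = 0.630. The tie-corrected standard error is √(0.953 × 126 / (12 × 63²)) = 0.0502. So z = 0.130 / 0.0502 = 2.58, and power is about Φ(2.58 − 1.96) = 0.73.

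**5. Simulation** (20,000 trials per case, 63 per arm, two-sided 0.05, shift 0.5 SD; Pearson chi-squared against tie-corrected Wilcoxon rank-sum):

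| Assumed control shares | Chi-squared | Rank-sum | Gap (points) |
|---|---|---|---|
| Five equal | 0.525 | 0.741 | 21.6 |
| 0.30/0.25/0.20/0.15/0.10 | 0.535 | 0.751 | 21.6 |
| 0.10/0.10/0.20/0.25/0.35 | 0.482 | 0.708 | 22.6 |
| 0.25/0.15/0.10/0.15/0.35 | 0.487 | 0.705 | 21.8 |
| Four equal | 0.556 | 0.728 | 17.2 |
| 0.15/0.15/0.25/0.45 | 0.496 | 0.668 | 17.2 |
| 0.30/0.30/0.40 | 0.575 | 0.677 | 10.2 |

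Further four-level runs with other shares gave 16 to 18 points. The four-level rows matter at 3 months: a participant who was insulin-naive at entry cannot yet have injected for more than six months, taking the visit as three months after the start.

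**6. Dependence on the effect.** At 0.3 SD the gap over these cases is about 7 to 15 points. With five equal shares it is 7 points at 0.2 SD (0.11 against 0.18) and 5 to 6 at 0.8 SD (0.93 against 0.98 to 0.99). With no effect, both tests reject about 5% of the time.

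**7. Where the order does not help.**
- Upward move between two adjacent answers only: four-level shares 0.10/0.10/0.35/0.45 becoming 0.10/0.10/0.15/0.65 give chi-squared about 0.62 and rank-sum about 0.40.
- No net shift: five equal shares becoming 0.10/0.15/0.50/0.15/0.10 give chi-squared about 0.86 and rank-sum about 0.06. Here chi-squared rejects for something that is not movement along the stages.

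**The case against.** The strongest reply is that the plan never says chi-squared will be used for this outcome. The sentence covers personal characteristics too, and sex and educational level are enough to explain why the test is listed. That stands: the use of chi-squared here is an inference. What remains is that no ordinal method is named and the only listed cross-sectional test for categories ignores order.

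Second, the mixed model is stated for the outcome variables without exception, and if the stages were scored it would use their order. This stands in part. The plan gives no scores, and the two items have different questions and answer sets, so the model does not clearly apply.

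Third, the order of the follow-up answers is imperfect. The third answer concerns forgetting injections, while the fourth and fifth differ only in time on insulin. A long-term user who sometimes forgets therefore ranks below a recent starter. None of the five answers plainly fits a patient who never started. A single shift along one scale is thus a real assumption. The reversal in step 7 is a plausible pattern for an intervention that works mainly on forgetting, and it is a move to a later stage, so an ordinal test is not always the stronger one.

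A reader might infer that the plan prescribes chi-squared for stage of change and so loses a fixed 10 to 23 points of power. The documents support neither part: the test is not assigned, and the size depends on shares and an effect that they do not give.

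**Conclusion.** The concern holds in conditional form. Stage of change has no clearly applicable method that uses its order. If chi-squared is used at each visit, its result cannot by itself show movement to later stages, and it has less power against a consistent ordered shift. With 63 per arm, assumed control shares and an assumed shift of 0.5 SD, the loss is about 21 to 23 points with five levels, 16 to 18 with four and 10 with three. It is smaller for smaller shifts, and it reverses when the effect is confined to two adjacent categories.

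The primary HbA1c analysis is not touched, and the error rate of the chi-squared test is sound. This is an inexpensive improvement worth considering, not a defect that threatens the trial's main conclusion.

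**What to change.** In the Data Analysis section, keep chi-squared for nominal characteristics such as sex. Add one sentence for stage of change: at each follow-up visit, fit a proportional-odds model of the follow-up stage with arm and baseline stage as terms, and report the common odds ratio with its 95% interval. The unadjusted form is a Wilcoxon rank-sum or linear-by-linear trend test. Show the stage-by-arm table beside the result. Entering baseline stage as a term also avoids the need for a common score between the two items.

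The change needs no new data, visits or patients. The downsides are small but should be stated. The model assumes a similar shift at every cut point. The order of the follow-up answers mixes adherence with time on insulin. Power is lower for shifts that are non-monotone or confined to two categories. The table lets a reader see such patterns.

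### Unadjusted follow-up tests between two non-randomised clinics stand beside a baseline-adjusted model, and the plan gives neither precedence

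*Combined protocol and SAP*

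**What the plan says.** On the design, the Study design section states: "The present study adopts quasi-experimental design". The arms are two clinics: "Patients with T2DM of an endocrinology clinic in southern Taiwan are assigned to the intervention arm", while "patients at another endocrinology clinic in southern Taiwan are placed in the control arm". It also defines the endpoint: "The main outcome variable is change in HbA1c levels".

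The Data Analysis section contains two kinds of between-arm comparison.

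- Unadjusted: the chi-squared test and the "independent t-test were used to compare differences in personal characteristics and outcome variables between the two groups before and after intervention". No baseline value or covariate enters these tests.
- Adjusted: "A linear mixed-effect model that adjusted for the demographic data and baseline outcome variables was used to examine the changing amount of outcome variables". The period compared starts with the 3-month visit and extends "to 12 months post-intervention between the intervention and control arms". On the random part: "Participants were considered as a random effect".

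The section closes with one significance threshold, p < .05, for everything. It does not name a primary analysis and does not call the unadjusted tests descriptive. Table 1 shows no baseline measurement for insulin injection adherence or self-efficacy. The stage-of-change question has three responses at baseline; at follow-up it is a different question with five responses.

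**The concern.** In a randomised trial a follow-up t-test is less efficient than a baseline-adjusted analysis, but it is unbiased. Here the arms are two clinics, and nothing makes their patients alike in expectation. The null hypothesis of the follow-up t-test is that the two clinics have equal levels at that visit, which differs from the hypothesis that the intervention has no effect. A difference that existed before the intervention can therefore appear as a significant result. If the intervention clinic starts worse, a real benefit can be hidden.

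The bias is present at any single visit, and no multiplicity correction removes it. Because the plan sets no order between the two analyses, a significant unadjusted HbA1c difference at 12 months could be reported as a planned result even where the adjusted model disagrees. The planned baseline comparison does not protect against this, since a non-significant test with these numbers says little about balance.

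**Working it through.** **Inputs from the documents.** The Samples section gives an effect size of 0.5 SD, α = 0.05, power 0.8, 63 per arm, 20% attrition and 76 per arm to recruit.

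**The plan's own figure.** n = 2 × (1.960 + 0.842)² / 0.5² = 62.8, so 63 per arm reproduces (two-sided, normal approximation). The stated 76 is 63 × 1.2 = 75.6, rounded up. Recruiting 76 and losing 20% leaves 76 × 0.8 = 60.8, so 61 per arm is used below.

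**Assumptions not in the documents.** The true effect is 0. The clinics differ by b SD at baseline. A fraction k of that difference, from 0.5 to 1.0, is still present at follow-up. The correlation r between baseline and follow-up is 0.3 to 0.7. One visit is examined at a time.

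**Step 1: unadjusted follow-up t-test.** The non-centrality is b × k × √(61/2), with 120 degrees of freedom and a two-sided 5% test. For b = 0.3, √30.5 = 5.523, so the non-centrality is 0.828 at k = 0.5 and 1.657 at k = 1.

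| b (SD) | k = 0.5 | k = 1 |
|---|---|---|
| 0.1 | 5.9% | 8.5% |
| 0.2 | 8.5% | 19.5% |
| 0.3 | 13% | 38% |
| 0.4 | 19.5% | 59% |

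**Step 2: baseline-adjusted comparison on the same assumptions.** Adjustment subtracts r × b, so the remaining bias is b × (k − r). The standard error is √((1 − r²) × 2/61), ignoring the small inflation from baseline imbalance. Rejection rates use the normal approximation, for b = 0.3:

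| r | SE | Bias, k = 1 | Rejects, k = 1 | Bias, k = 0.5 | Rejects, k = 0.5 |
|---|---|---|---|---|---|
| 0.3 | 0.173 | 0.21 | 23% | 0.06 | 6% |
| 0.5 | 0.157 | 0.15 | 16% | 0.00 | 5% |
| 0.7 | 0.129 | 0.09 | 11% | −0.06 | 7.5% |

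With full persistence the unadjusted test rejects 38% of the time and the adjusted comparison 11% to 23%. With half persistence the figures are 13% and about 5% to 7.5%.

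**Step 3: the opposite direction.** Take a true effect of 0.5 SD and an intervention clinic that starts 0.3 SD worse. The visible difference at follow-up is 0.5 − 0.15 = 0.35 SD at k = 0.5, or 0.5 − 0.3 = 0.2 SD at k = 1. Power of the unadjusted test with 61 per arm falls from 78% to 48% or 19%.

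**Step 4: the baseline test as a safeguard.** With 76 per arm and b = 0.3, the non-centrality is 0.3 × √38 = 1.849 on 150 degrees of freedom, and power is 45%. A baseline difference of this size would be missed more often than found.

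**The case against.** A reader might infer that the plan as a whole treats any baseline clinic difference as an intervention effect. The documents do not support that. The same section plans a mixed model that adjusts for demographic data and the baseline outcome and compares change between arms. The main outcome is change in HbA1c, which is what that model addresses; the t-tests compare levels. No sentence says that conclusions about the intervention come from the t-tests, and the single p < .05 rule also covers the baseline and within-group tests, so it does not by itself give the t-tests equal standing. All of this stands. It narrows the point to the unadjusted follow-up tests and the missing order of precedence.

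A reader might also infer that dropping the unadjusted tests restores a 5% error rate. It does not. With one clinic per arm and only participants as a random effect, clinic differences not captured by the covariates stay confounded with the intervention under either analysis. Part of the upper end in step 1 is therefore a limit of the design, as step 2 shows.

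The sizes of baseline difference, persistence and correlation are assumed, and the rates describe one test in isolation. Both clinics apply the same HbA1c entry threshold of 8.5%, which may narrow the difference for the main outcome but does not ensure balance. Finally, simply deleting every follow-up t-test and chi-squared test would leave gaps: adherence and self-efficacy have no baseline to adjust for, and stage of change is categorical, so a linear model does not suit it.

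**Conclusion.** The concern holds in a limited form. The plan includes unadjusted between-arm tests of follow-up outcomes in a non-randomised two-clinic design, at p < .05, and does not rank them below the adjusted model. Those tests do not isolate the intervention effect. With no true effect, 61 per arm and an assumed 0.3 SD baseline difference of which half to all persists, they reject 13% to 38% of the time. When the difference persists in full, the baseline-adjusted comparison rejects 11% to 23% of the time for correlations of 0.3 to 0.7, so it is the less biased of the two but not free of bias. The direction of the finding needs only that the clinics differ at baseline and that some of the difference carries forward; its size depends on the assumed values. A suitable model is already planned, so what is missing is precedence, explicit handling of three outcomes, and a stated limitation.

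**What to change.** Revise the Data Analysis section as follows.

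- **Continuous outcomes with a baseline value:** name the adjusted mixed model, with its covariates listed, as the sole basis for between-arm conclusions. Restrict the independent t-tests to describing baseline. Show raw follow-up means by arm without p-values.
- **Insulin adherence and self-efficacy:** compare arms with the model adjusted for demographic data, and label the result as not adjusted for baseline.
- **Stage of change:** either keep a categorical comparison labelled descriptive and unadjusted, or fit a categorical model that adjusts for baseline stage.
- **Limitation:** state that with one clinic per arm, clinic differences beyond the measured covariates cannot be separated from the intervention effect.

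The cost is a few sentences, fewer p-values to report and slightly more modelling work. No additional data or participants are needed.

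### Change in stage of change is a secondary outcome, but it is asked with two unlike items and no common coding, so the linear change analysis is not defined for it

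*Combined protocol and SAP*

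**What the plan says.** The Study design section lists the secondary outcomes as changes: "while the change in stage of change, in insulin injection adherence, in appraisal of insulin injection", and so on. Table 1 schedules "Stage of change for insulin injection" at baseline and at 3, 6 and 12 months.

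The item is described under Demographic data & disease characteristics. At baseline, participants say how they would respond if the doctor recommended insulin now. The three answers stand for "three early stages of change — precontemplation, contemplation, and preparation". Later the item changes: "At the 3, 6, and 12 months post-intervention, the question was" about the present status of injecting. Its five answers, in listed order and paraphrased except where quoted, are:

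1. "taking insulin injection previously, but now is stop insulin injection and never consider to receive insulin injection again"
2. stopped, but thinking of restarting within six months
3. "still receive insulin injection but sometimes forget to inject"
4. injecting without interruption for under six months
5. injecting without interruption for over six months

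These five answers are given neither stage names nor scores.

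The Data Analysis section gives three kinds of comparison:
- chi-squared and independent t-tests between groups, before and after the intervention;
- paired t-tests within groups across the visits;
- a linear mixed model, adjusted for demographic data and the baseline value, that "was used to examine the changing amount of outcome variables from baseline to 3 months" and to the later visits.

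No method is tied to a named outcome.

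**The concern.** A change score needs one scale at both ends. Here one end is an intention expressed before any insulin use, and the other is a report of current or past injecting. The plan does not say which follow-up answer corresponds to which stage, what numbers the answers receive, or why the steps between them should be equal. The analyst would have to settle this, possibly after seeing the data.

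The follow-up answers also leave a gap. Answers 1 and 2 presuppose earlier insulin use, and answers 3 to 5 describe current use. A participant who never began has no truthful answer. The Introduction makes starting insulin the target of the intervention, and the baseline item expects some participants never to have considered it, so this group may well exist. Such participants would be either missing or misclassified as having stopped.

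At stake is whether the arm comparison on this secondary outcome can be read at all.

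**Working it through.** The plan states no figure for this outcome, so there is none to reproduce. The check is whether the change score is fixed by the text and, if not, how much the result moves.

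**Inputs from the plan.** Three ordered baseline answers, five follow-up answers, and a linear analysis of change.

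**Assumed inputs.** The plan assigns no codes, so two plausible sets are compared. Baseline is coded 1, 2, 3 in both.
- Coding A, listed order: follow-up answers = 1, 2, 3, 4, 5.
- Coding B, anyone injecting counted as at least in the action stage: follow-up answers = 1, 2, 4, 4, 5.

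**Step 1: one participant.** Change = follow-up code minus baseline code, for someone who now injects with lapses (answer 3).

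| Baseline stage | Coding A | Coding B |
|---|---|---|
| Precontemplation (1) | 3 - 1 = +2 | 4 - 1 = +3 |
| Contemplation (2) | 3 - 2 = +1 | 4 - 2 = +2 |
| Preparation (3) | 3 - 3 = 0 | 4 - 3 = +1 |

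The bottom row is a person who went from no insulin to insulin. Coding A records no movement, and coding B records one step. The plan does not choose between them.

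**Step 2: the arm difference.** Assume equal baselines, so that the difference in mean change equals the difference in mean follow-up code. Assume also that everyone has started insulin and that the shares giving answers 1 to 5 at one visit are 15/5/10/70/0% (intervention) and 5/5/60/30/0% (control). These shares are illustrative only.

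- Coding A, intervention: 0.15×1 + 0.05×2 + 0.10×3 + 0.70×4 = 3.35
- Coding A, control: 0.05×1 + 0.05×2 + 0.60×3 + 0.30×4 = 3.15
- Difference under A: 3.35 - 3.15 = **+0.20**
- Coding B, intervention: 0.15×1 + 0.05×2 + 0.10×4 + 0.70×4 = 3.45
- Coding B, control: 0.05×1 + 0.05×2 + 0.60×4 + 0.30×4 = 3.75
- Difference under B: 3.45 - 3.75 = **-0.30**

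**Step 3: the range.** The codings differ by one unit on answer 3 only. Moving from A to B therefore shifts the arm difference by the intervention share minus the control share giving that answer. Here that is 0.10 - 0.60 = -0.50, and +0.20 - 0.50 = -0.30, as found. With equal shares the shift is 0. With the control share 10 or 25 percentage points higher, it is -0.10 or -0.25. A coding-A difference of +0.20 changes sign once the control share exceeds the intervention share by more than 20 points.

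**Step 4: the available methods.** The mixed model and the paired t-test both need numeric codes. The chi-squared test does not, but as described it compares groups and neither analyses change nor uses baseline stage.

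**The case against.** The strongest reply is that the plan never says stage of change enters the linear model. It is covered only by the general reference to outcome variables, and that reference cannot be universal: Table 1 shows no baseline for adherence or self-efficacy. Stage is the one secondary outcome recorded as named categories, so the chi-squared test may have been meant for it. This stands in part. A reader might infer that the plan expressly commits stage to a linear model, and the text does not go that far. But stage does have a baseline, nothing excepts it, and the chi-squared test is not assigned to it. On that reading too, the declared outcome, a change, has no stated analysis.

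A second reply is that the five follow-up answers may be meant to match the five stages in the intervention tables. That is plausible, and a stated mapping could make change readable as ordered movement. So the documents do not support the stronger claim that the difference can have no meaning. The mapping is simply not given, and even with it, equal codes would describe different states and equal spacing would be unsupported.

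A third, technical reply is that in a linear model of change adjusted for baseline as a linear term, the arm coefficient is the same as in a model of the follow-up value, so the baseline codes matter little to the arm contrast. That is right. It does not rescue the analysis, because the reversal in the working comes from the follow-up codes alone, and the paired t-tests gain nothing from it.

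Two further inferences should be resisted. The mixed model is not the only stated analysis of change, since the paired t-tests address it within groups. And the step from under to over six months of injecting is not a product of the calendar alone: it requires continued injecting, which the intervention aims to support.

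**Conclusion.** The concern holds in this form: as written, the numeric change in stage of change is not defined or interpretable, and the follow-up item has no place for a participant who never started insulin. The differing items, the missing mapping and the missing category can be read directly from the plan. That stage falls under the linear change analysis rests on the unqualified wording of the Data Analysis section.

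The size cannot be estimated from the documents. The scores of 0 and +1 and the arm differences of +0.20 and -0.30 depend on assumed codes and shares. They show that the sign can turn on an unstated choice, not that it will. A reader might take the zero score as what the plan produces; it appears only under listed-order codes, which the plan does not prescribe.

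The point affects one secondary outcome, and the plan sets no hierarchy among the secondary outcomes. The primary HbA1c analysis is untouched. The change should be made, but the trial's main conclusion does not depend on it.

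**What to change.** - State that stage of change is excluded from the linear change model and the paired t-tests.
- Put participants who never started insulin in their own follow-up category, and pre-specify the order of all categories, including where this one sits. If the question can no longer be altered, the regimen details collected once injecting begins may help to identify these participants.
- Analyse follow-up stage with a cumulative-logit model containing arm, visit, arm-by-visit and baseline stage as a three-level categorical covariate. Account for repeated measures within participant, or fit the model separately at each visit.
- Report alongside it, by arm and visit, the proportion of all enrolled participants currently injecting, counting never-starters as not injecting.

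The cost is mainly wording in the Data Analysis section and a standard ordinal model. The small downside is that results are odds ratios and proportions rather than mean stage changes.
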